3 LIST OF ABBREVIATIONS

ACS:	Acute coronary syndrome
AE:	Adverse event
AESI:	Adverse event of special interest
ALP:	Alkaline phosphatase
ALT:	Alanine aminotransferase
ANCOVA:	Analysis of covariance
Apo A-1:	Apolipoprotein A-1
Apo B:	Apolipoprotein B
AST:	Aspartate aminotransferase
BMS:	Bare metal stent
CEC:	Clinical Event Committee
CHD:	Coronary heart disease
CPK:	Creatine phosphokinase
CRF:	Case report form
CRP:	C-reactive protein
CV:	Cardiovascular
DBP:	Diastolic blood pressure
DES:	Drug eluting stent
e-CRF:	Electronic Case Report Form
EEM:	External elastic membrane
EOT:	End of treatment
FH:	Familial hypercholesterolemia
HbA1c:	Hemoglobin A1c
HDL-C:	High-density lipoprotein cholesterol
heFH:	Heterozygous familial hypercholesterolemia
HLGT:	High level group term
HLT:	High level term
HRT:	Hormonal replacement therapy
hs-CRP:	High sensitive C-reactive protein
IEC:	Independent ethics committee
IMP:	Investigational medicinal product
IRB:	Institutional review board
IVUS:	Intravascular ultrasound
JAS:	Japan Atherosclerosis Society
LDH:	Lactate dehydrogenase
LDL-C:	Low-density lipoprotein cholesterol
LDL-R:	Low-density lipoprotein receptor
LLT:	Low level term
LMT:	Lipid modifying therapy
Lp(a):	Lipoprotein (a)
LS:	Least square

MedDRA:	Medical dictionary for regulatory activities
MI:	Myocardial infarction
mITT:	Modified intent-to-treat
MMRM:	Mixed-effect model with repeated measures
NIMP:	Noninvestigational medicinal product
non-FH:	Nonfamilial hypercholesterolemia
non-HDL-C:	Non-high-density lipoprotein cholesterol
NSTEMI:	Non ST-elevation myocardial infarction
OCT:	Optical coherence tomography
PAV:	Percent atheroma volume
PCI:	Percutaneous coronary intervention
PCSA:	Potentially clinically significant abnormality
PCSK9:	Proprotein convertase subtilisin kexin type 9
PT:	Preferred term
Q2W:	Every 2 weeks
SAE:	Serious adverse event
SAP:	Statistical analysis plan
SBP:	Systolic blood pressure
SC:	Steering Committee
SE:	Standard error
SoC:	Standard of care
SOC:	System organ class
STEMI:	ST-elevation myocardial infarction
TAV:	Total atheroma volume
TC:	Total cholesterol
TEAE:	Treatment-emergent adverse event
TG:	Triglyceride
ULN:	Upper limit of normal range
WOCBP:	Women of childbearing potential
γ GT:	Gamma-glutamyl transpeptidase

4 INTRODUCTION AND RATIONALE

Alirocumab is a fully human monoclonal antibody that binds proprotein convertase subtilisin kexin type 9 (PCSK9).

Alirocumab has been approved for manufacturing and sales in Japan. The approved indications, and dosage and administration are as follows:

- **Drug indications:** Familial hypercholesterolemia and hypercholesterolemia nevertheless it is limited to cases at high cardiovascular (CV) risk and with inadequately controlled despite of taking HMG-CoA reductase inhibitors.
- **Dosage and Administration:** The usual adult dosage is 75 mg of alirocumab (genetical recombination) administered subcutaneously once every 2 weeks (Q2W). In case of an insufficient response, the dosage can be increased to 150 mg.

Detailed information of alirocumab is described in the latest version of Package Insert.

Alirocumab is also referred to as SAR236553/REGN727. However, for this study, ODYSSEY J-IVUS (ALIROL08069), it will be referred to as Praluent®, since alirocumab has already been approved in Japan.

Background on patient populations:

Patients with recent acute coronary syndrome (ACS) are at very high risk for suffering recurrent coronary events. In approximately 10% of patients with ACS, CV death, recurrent myocardial infarction (MI), or stroke, occur within 1 year (3). Driven by the results of large clinical trials, early intensive statin therapy has become endorsed as a treatment recommendation (4, 5) for patients with ACS (6) to prevent the recurrent events. The use of high-dose statins has been largely demonstrated to be safe and well tolerated in Western countries (7). The strong and direct association between achieved low-density lipoprotein cholesterol (LDL-C) levels with statins, HMG-CoA reductase inhibitors, and the risk of coronary heart disease (CHD), and CHD risk reduction by lowering LDL-C level with statins has been reported. In recognition of the benefits of intensive lipid-lowering therapy, the current European guidelines and the Adult Treatment Panel (ATP) III guidelines recommend the lowering of LDL-C levels to either below 70 mg/dL or to at least achieve a 50% reduction from baseline levels in patients at high CV risk (8, 9, 10).

IMPROVE-IT (Improved Reduction of Outcomes: Vytorin Efficacy International Trial) demonstrated an incremental benefit of adding ezetimibe to standard statin therapy to reduce CV events (11). The benefit of further LDL-C reduction with alirocumab on top of statin therapy on patient CV outcomes is expected to be demonstrated in the ongoing ODYSSEY Outcomes trial (EFC11570). On the other hand epidemiological studies show lower CV event rates and higher cerebrovascular event rates in the Japanese population as compared to Western populations. In the REACH (Reduction of Atherothrombosis for Continued Health) registry, a correlation exists between being Japanese and lower CV risk at levels that are similar to that of statin use and CV

risk reduction in Western populations (12), which suggests the need to take the differences in ethnicity into consideration. Thus, there is a need to conduct an outcome or outcome surrogate marker study targeting the Japanese population to demonstrate the benefit of intensive LDL-C lowering in Japanese population.

Introduction to intravascular ultrasound (IVUS) coronary plaque measurements:

Advances in arterial wall imaging have enhanced the ability to directly visualize atherosclerotic plaque. While angiography has been widely used to quantify the extent of obstructive disease both in clinical practice and trials that evaluated anti-atherosclerotic therapies, it does not image the artery wall, the site in which plaque accumulates. Accordingly, use of wall-based imaging approaches provides the potential for more precise assessments of atherosclerotic plaque.

Intravascular ultrasound (IVUS) generates high resolution images of the full thickness of the artery wall and as a result currently provides the most accurate quantitation of plaque burden (13). Serial IVUS imaging has been employed to evaluate the effect of LDL-C lowering on plaque regression (14, 15, 16). Many studies have demonstrated the effectiveness of intensive statin therapies. The Study of Coronary Atheroma by Intravascular Ultrasound: Effect of Rosuvastatin versus Atorvastatin (SATURN) compared the effects of statin on the progression of coronary atherosclerosis of the highest doses of atorvastatin with those of rosuvastatin (17, 18). The rosuvastatin group achieved lower LDL-C levels (62.6 vs. 70.2 mg/dL) and higher high-density lipoprotein cholesterol (HDL-C) levels (50.4 vs. 48.6 mg/dL) compared with the atorvastatin group. The change in percent atheroma volume as a primary endpoint decreased in both groups consistent with plaque regression, the difference between groups not reaching statistical significance. In contrast, the secondary endpoint, change in total atheroma volume (TAV), demonstrated greater regression in the rosuvastatin treated patients. Approximately two-thirds of patients in the study demonstrated regression, reinforcing the hypothesis that aggressively lowering LDL-C to levels of 70 mg/dL and below offered significant plaque reduction. Furthermore, a meta-analysis of 6 clinical IVUS trials demonstrated a direct relationship between the burden of coronary atherosclerosis, its progression, and adverse CV events. These data support the use of atherosclerosis imaging with IVUS in the evaluation of novel anti-atherosclerotic therapies (19).

Japanese cardiologists use IVUS imaging as part of their standard coronary intervention throughout the country and many IVUS trials have been conducted (1, 18, 20, 21). This universal use of IVUS is a unique to Japanese practice, and this condition is suitable to efficiently conduct a nation-wide study using IVUS imaging. Most recently PRECISE-IVUS (Plaque Regression with Cholesterol Absorption Inhibitor or Synthesis Inhibitor Evaluated by Intravascular Ultrasound) trial demonstrated greater plaque regression by combination therapy of ezetimibe and atorvastatin compared to atorvastatin monotherapy in patients with CHD (2).

The SATURN and the PRECISE-IVUS studies showed greater plaque regression in ACS patients when compared with non-ACS patients. Since it is suggested that patients with ACS have high initial clinical risk but their disease substrate is likely to be improved, they are considered as the patient population who can get the greatest benefit from strong lipid lowering therapy (2, 22).

Introduction to PCSK9:

PCSK9 belongs to the subtilisin family of serine proteases and is highly expressed in the liver. PCSK9 is involved in regulating the levels of the low-density lipoprotein receptor (LDL-R) protein (23, 24). Once PCSK9 is secreted into plasma, it directly binds to the LDL-R and promotes its degradation. The increased degradation of LDL-Rs leads to a reduced LDL-C removal and, therefore higher LDL-C circulating levels. Experiments with mice have shown that increasing PCSK9 protein levels decreases levels of LDL-R protein in the liver, while PCSK9 knockout mice have increased levels of LDL-R protein in the liver (25, 26). In humans, PCSK9 mutations have been identified: the gain-of-function mutations are rare and cause an autosomal dominant form of severe hypercholesterolemia and premature CHD, whereas loss-of-function mutations are more common and are associated with reduced plasma levels of LDL-C and protection from developing cardiovascular disease (27, 28). One report from the Japanese population found the individual heterozygous for W428X mutation of PCSK9 had 70.4 mg/dL of plasma LDL-C, corresponding to a 44% decrease from the average LDL-C level (126.8 mg/dL) in the untreated population. This observation is consistent with the finding that the two African-American nonsense mutations were associated with a 40% reduction in plasma LDL-C levels (29). Therefore blocking PCSK9 binding to the LDL-R can potentially benefit patients with hypercholesterolemia by decreasing their plasma LDL-C levels. In addition, PCSK9 messenger ribonucleic acid (mRNA) and protein levels are increased in response to statins, potentially attenuating their cholesterol-lowering effect (30).

Introduction to Alirocumab:

Alirocumab binds with high affinity and specificity to PCSK9, which, in turn, can no longer bind LDL-Rs. By inhibiting the binding of PCSK9 to LDL-Rs, alirocumab prevents the PCSK9-induced microsomal LDL-R degradation within the hepatocytes, thus increases the density of LDL-Rs on hepatocytes, thereby lowering LDL-C.

Results from phase 1 and 2 overseas studies have demonstrated that treatment with alirocumab has a significant LDL-C lowering effect in patients with LDL-C \geq 100 mg/dL (2.59 mmol/L) who had either nonfamilial hypercholesterolemia (non-FH) (administered alone or in combination with a statin) or heterozygous familial hypercholesterolemia (heFH) (administered in combination with a statin, with or without ezetimibe). Alirocumab was generally well tolerated. LDL-C reduction was associated with consistent reduction in total cholesterol (TC), apolipoprotein B (Apo B), non-high-density lipoprotein-cholesterol (non-HDL-C) and Apo B/apolipoprotein A-1 (Apo A-1) ratio. A trend for an increase in HDL-C and for a decrease in lipoprotein (a) (Lp(a)) was also seen. Results for triglycerides (TGs) were not conclusive due to very high variability and relatively small sample sizes. A dose-finding phase 2 study (DFI12361) conducted in Japanese patients showed similar results observed in the oversea studies.

Japanese Phase 3 study (EFC13672):

In EFC13672, administration of alirocumab Q2W for 52 weeks as an add-on to stable statin therapy with or without other lipid modifying therapies (LMTs) was investigated in 41 patients with heFH and 175 patients with hypercholesterolemia who have high CV risk, who had not achieved target LDL-C level on statin therapy. An up-titration scheme was applied, with alirocumab 75 mg Q2W as the initiation dose with up-titration to 150 mg Q2W from Week 12, if LDL-C level at Week 8 is higher than the target level. Dose/dose regimens in the Japanese phase 3 study were selected based on the results obtained in the Japanese phase 2 study (DFI12361).

EFC13672 enrolled patients with heFH with LDL-C ≥ 100 mg/dL (2.59 mmol/L) or patients with non-FH with LDL-C ≥ 100 mg/dL (2.59 mmol/L) with a history of documented CHD, or patients with non-FH with LDL-C ≥ 120 mg/dL and categorized in primary prevention category III. These cut-off LDL-C levels were aligned with the LDL-C target level recommended in the Japan Atherosclerosis Society (JAS) guidelines (31). In the JAS guidelines, the treatment goal for the secondary prevention is set as < 100 mg/dL. Since heFH is a high risk disease for the development of cardiovascular disease, it can be considered as equivalent to the secondary prevention. The treatment goal for LDL-C in heFH is set as < 100 mg/dL as well. When the goal cannot be achieved in heFH cases, 50% or more reduction of LDL-C from baseline can be used as the alternative goal. For the patients who are primary prevention category III, the treatment goal for LDL-C is established as < 120 mg/dL. The primary prevention category III is defined as follows:

- Non-FH patients who have any of 1) diabetes, 2) chronic kidney disease (CKD), 3) non-cardiogenic ischemic stroke, or 4) peripheral artery disease (PAD)
- A 10-year fatal CHD risk SCORE calculated using NIPPON DATA 80 $\geq 2\%$
- A 10-year fatal CHD risk SCORE calculated using NIPPON DATA 80 $\geq 0.5\%$ and $< 2\%$, and have 1 or more of the following criteria
 - Hypo high-density lipoprotein cholesterolemia (< 40 mg/dL)
 - Family history of premature coronary artery disease (first-degree relative and male: < 55 -year-old, female: < 65 -year-old)
 - Impaired glucose tolerance (defined as a fasting blood glucose [FBG] < 126 mg/dL [7.0 mmol/L], and a 2-hour post glucose challenge value ≥ 140 mg/dL [7.8 mmol/L] and < 200 mg/dL [11.1 mmol/L] (oral glucose tolerance test [OGTT])).

Efficacy (EFC13672):

In EFC13672, alirocumab or placebo were administered Q2W for 52 weeks to 216 patients with hypercholesterolemia (including 41 patients with heFH) who were under treatment with statin and had not achieved the target LDL-C level. The administration was initiated with 75 mg and dose was up-titrated to 150 mg at Week 12 in the patients who did not achieve the target LDL-C level at Week 8. Among 140 patients who received alirocumab at Week 12 in the alirocumab group, 2 patients received up-titration. The least square (LS) mean differences versus placebo in the percent change in LDL-C from baseline to Week 12 and Week 24 were -61.5% and -64.1% respectively, showing that the statistically significant decrease was observed at Week 24 (primary

efficacy endpoint, $p < 0.0001$). The effect persisted up to Week 52 (LS mean present change from baseline in the alirocumab group, -62.5%).

Safety (EFC13672):

Alirocumab was well tolerated throughout the treatment period. Treatment-emergent adverse events (TEAEs) were reported in 90.9% of patients in the alirocumab group and 83.3% of patients in the placebo group. Ten patients (7.0%) in the alirocumab group and 9 patients (12.5%) in the placebo group experienced at least 1 treatment-emergent serious adverse event (SAE). There were no deaths reported. Seven patients (4.9%) in the alirocumab group and 4 patients (5.6%) in the placebo group experienced at least 1 TEAE leading to permanent investigational medicinal product (IMP) discontinuation.

Overall, 29 patients (20.3%) in the alirocumab group and 8 patients (11.1%) in the placebo group reported at least 1 TEAE that was considered by the Investigator to be related to the IMP. The most frequently reported TEAE considered to be related to the IMP was injection site reaction (18 patients [12.6%] in the alirocumab group and 3 patients [4.2%] in the placebo group). All the remaining TEAEs considered to be related to the IMP were reported in a single patient each.

Further details on alirocumab are provided in the Package Insert of Praluent®.

Rationale for protocol design in this study:

The objective of the present study is to evaluate the ability of alirocumab to progress/regress coronary atherosclerotic plaque in patients who experienced an ACS event and despite statin therapy failing to reach the goals as defined in the guidelines for these high risk patients of recurrence. As a phase 4 study, the dose regimen in this study has to be in line with the approved regimen in Japan, which is starting Praluent® at 75 mg Q2W with up-titration to 150 mg Q2W if patients do not reach their target LDL-C level.

For this randomized, open-label, blinded IVUS analysis, multicenter study, it is estimated that approximately 200 patients will be enrolled with a treatment period of 9 months and a total duration of 9 to 10 months. Despite stable statin therapy, hypercholesterolemia patients who suffer ACS events and whose LDL-C ≥ 100 mg/dL will be enrolled this study. Or, if patients are not on any statin therapy at ACS onset, either atorvastatin 10 mg/day or rosuvastatin 5 mg/day is started, and the patients whose LDL-C is not adequately controlled with statin (in principle, LDL-C target level ≥ 100 mg/dL, but this may not apply if the responsible physician considers the LDL-C level inadequate on statin. Patients who have LDL-C < 70 mg/dL cannot be enrolled) at 2 to 4 weeks after the ACS diagnosis will be enrolled this study. Within 4 weeks of the index ACS diagnosis, patients will be randomized to either alirocumab arm (atorvastatin ≥ 10 mg/day or rosuvastatin ≥ 5 mg/day plus Praluent® 75 mg Q2W with/without other LMTs) or standard of care (SoC) arm (atorvastatin ≥ 10 mg/day or rosuvastatin ≥ 5 mg/day with/without other LMTs). At Week 12, if LDL-C does not reach < 100 mg/dL, Praluent® will be up-titrated to 150 mg Q2W in the alirocumab arm, and dose up of atorvastatin or rosuvastatin or adding other LMTs will be considered in the SoC arm.

Treatment duration of 9 months was designed based on previous Japanese studies including ESTABLISH (18), JAPAN-ACS (20) and PRECISE-IVUS (2), each study duration was 6 months, 8-12 months and 9-12 months, respectively. This is based on Japanese standard procedure for follow-up to coronary angiography 8-10 months after the ACS onset. Also, keeping 8-10 months study duration makes it feasible to align with standard Japanese IVUS studies. If the study goes beyond this standard duration, then a very high drop-out rate is expected. Compared to the studies done in Cleveland Clinic, the study duration in Japan are shorter and yet still sufficiently proved the benefit of LDL-C reduction on disease progression. This may be because differences in target population (ACS vs. non-ACS) and target vessel (culprit vessel vs. non-culprit vessel). It is also noted that diabetes population is also well known high risk population and studies suggest more benefit of intensive LDL-C lowering in diabetes population compared to the non-diabetes population (1, 32, 33).

The proposed primary efficacy endpoint is the effect of alirocumab arm compared to SoC arm on the percent change in normalized TAV measured by IVUS. Considering the differences in IVUS study methods of Japan with the Cleveland Clinic, sample size is more appropriately calculated based on Japanese IVUS study results. Percent change in TAV has been predominantly used as a primary endpoint in Japanese IVUS studies. Based on the results in ZEUS and PRECISE-IVUS studies, it is assumed that difference in percent change in normalized TAV from baseline between alirocumab arm and SoC arm is 8%, the common standard deviation is 15% (1, 2). Considering that absolute change in percent atheroma volume (PAV) has been employed in most US IVUS studies as a primary endpoint, comparison of change in PAV between arms will be analyzed as a key secondary endpoint (34).

Based on previous Japanese IVUS studies results, IVUS parameters including primary efficacy endpoint, and percent change in TAV, will be assessed at Week 36 since this is considered sufficient to provide efficacy information of alirocumab on atherosclerosis disease progression/regression in this study (1, 2, 18, 20, 21). This treatment duration should also provide a sufficient duration of exposure to appreciate tolerability and safety profiles for alirocumab in the ACS setting. The effect of alirocumab on lipid parameters will also be assessed at Week 36 in this study.

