
STUDY POPULATION
 
Main selection criteria
	
Main inclusion criteria:
 
I 01. Patients hospitalized for ACS (ST-elevation myocardial infarction [STEMI], non ST-elevation myocardial infarction [NSTEMI], unstable angina).
 
I 02. LDL-C ≥ 100 mg/dL at ACS diagnosis (either by Friedewald method or direct method measured at each study site).:
a) Patients who have already been on any statin therapy at ACS onset. If the statin is not atorvastatin or rosuvastatin, statin will be changed to either atorvastatin ≥ 10 mg/day or rosuvastatin ≥ 5 mg/day immediately after the ACS diagnosis based on Investigators' medical judgment.b) If patients have not been on any statin therapy at ACS onset, either atorvastatin 10 mg/day or rosuvastatin 5 mg/day is started immediately after the ACS diagnosis, and LDL-C is not adequately controlled with statin at 2 to 4 weeks after the ACS diagnosis (in principle, LDL-C target level ≥ 100 mg/dL, but this may not apply if the responsible physician considers the LDL-C level inadequate on statin. Patients who have LDL-C <70 mg/dL cannot be enrolled).
 
I 03. Patients who has stenosis of at least 50% on coronary angiography within 1 week after the ACS onset, and has analyzable coronary IVUS image. The evaluated segment of IVUS is a segment where a physician considers the IVUS imaging is possible (regardless of culprit vessels or not culprit vessels) other than the culprit lesions.
 
I 04. Patients aged ≥ 20 years old at ACS diagnosis.
 
I 05. Patients who meet any of the following conditions:
- Negative hepatitis B virus surface antigen, negative hepatitis B virus total core antibody, and negative hepatitis C virus antibody.- Negative hepatitis B virus surface antigen, positive hepatitis B virus total core antibody, negative hepatitis B virus DNA, and negative hepatitis C virus antibody.
 
I 06. Written informed consent.

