STATISTICAL CONSIDERATIONS	
Sample size determination: The study is expected to enroll approximately 200 patients. Based on the results of ZEUS(1) and PRECISE-IVUS(2) studies, it is assumed that difference in percent change in normalized TAV from baseline between alirocumab arm and SoC arm is 8%, and the common standard deviation of percent change in normalized TAV is 15%. Under the assumption, a sample size of 150 patients (75 in the alirocumab arm and 75 in the SoC arm) will have 90% power to detect the treatment difference with two-sided significance level of 5%. Assuming that proportion of non-evaluable primary endpoint is 25%, it is considered that 200 patients (100 in the alirocumab arm and 100 in the SoC arm) will be needed.
 
Analysis population: Randomized population includes all patients who have been allocated to a randomized treatment and recorded in the registration center database, regardless of whether a study drug was used or not. The primary efficacy analysis population will be the modified intent-to-treat (mITT) population, defined as the randomized population who takes at least one dose or part of dose of study drug and has an available value of normalized TAV before randomization and after 24 weeks of treatment. Patients in the mITT population will be analyzed according to the treatment arm allocated by randomization. The safety population consists of patients of randomized population who actually received at least one dose or partial dose of study treatment. The safety population will be analyzed according to the treatment actually received.
 
Primary analysis: The percent change in normalized TAV will be analyzed using an analysis of covariance (ANCOVA) model with treatment arm and randomization strata as fixed effects, and the baseline normalized TAV as covariate.
 
Analysis of Key secondary efficacy endpoints: Analysis of key secondary efficacy endpoint will be performed on the mITT population considering corresponding baseline value as covariate, in the same manner as for the primary endpoint.
 
Multiplicity adjustment: A hierarchical procedure will be used to control the type I error and to handle multiple endpoints. If the primary endpoint analysis is significant at the two-sided 5% alpha level, the key secondary

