11 STATISTICAL CONSIDERATIONS

11.1 DETERMINATION OF SAMPLE SIZE

The study is expected to enroll approximately 200 patients. The sample size calculations are based on the primary efficacy variable of percent change in normalized TAV from baseline to Week 36.

Based on the results of ZEUS (1) and PRECISE-IVUS (2) studies, it is assumed that difference in percent change in normalized TAV from baseline between alirocumab arm and SoC arm is 8%, and the common standard deviation of percent change in normalized TAV is 15%.

Under the assumption, a sample size of 150 patients (75 in the alirocumab arm and 75 in the SoC arm) will have 90% power to detect the treatment difference with two-sided significance level of 5%. Assuming that proportion of non-evaluable primary endpoint is 25%, it is considered that 200 patients (100 in the alirocumab arm, 100 in the SoC arm) will be needed.

As the ANCOVA model will be used for primary analysis, the power should be somewhat higher due to reduced estimate variability versus the two-sample t-test.

Calculations were made using SAS 9.4

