### ***Disease characteristics at baseline***

Specific disease history includes:

- The index ACS subtype (acute ST-segment elevation myocardial infarction [STEMI], acute non ST-segment elevation myocardial infarction [NSTEMI], unstable angina [UA])
- Time from the index ACS diagnosis to randomization (in weeks), quantitatively and in category <2, ≥2 to <4, ≥4 weeks
- Revascularization procedure associated with the index ACS event (PCI or CABG)
- Time from the revascularization procedure to randomization (in weeks)
- Types of stents placed at the PCI (bare metal stent [BMS], drug eluting stent [DES] or both).
- Location of ACS culprit vessels
- Location of analyzed IVUS imaging vessels (RCA, LAD, LCX, Other)
- New cardiovascular events occurring after the index ACS diagnosis and before randomization, selected using e-CRF specific tick box on the adverse event page.
- Type of hypercholesterolemia:
  - Heterozygous familial hypercholesterolemia (heFH);
  - Non-familial hypercholesterolemia (non-FH);
  - Unknown;
- For heFH patients:
  - Time from diagnosis of heFH (years);
  - Diagnosis made by genotyping (Yes, No);
- For non-FH patients:
  - Time from diagnosis of hypercholesterolemia (years);
  - Fredrickson classification of hyperlipoproteinemia (IIa, IIb, IV);
- The background lipid modifying therapy (LMT) regimen at ACS diagnosis, as reported in the “Previous Lipid Modifying Therapy” e-CRF page, will be summarized using the following categories:
  - Any LMT
  - Any statin by daily dose
    - Atorvastatin, rosuvastatin, pravastatin, simvastatin, fluvastatin, pitavastatin
  - LMT other than statin
    - Ezetimibe

Fibrate

- Fenofibrate
- Bezafibrate
- Other
- Other

- The background lipid modifying therapy regimen at randomization, as reported in the “Previous Lipid Modifying Therapy” e-CRF page, will be summarized as those at ACS diagnosis.

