### ***Subgroup analyses (Stratified analyses)***

To assess the homogeneity of the treatment effect across various subgroups, treatment group-by-subgroup factor interaction terms and a subgroup factor term will be added in the primary ANCOVA model. LS means difference versus SoC will be provided, as well as the corresponding SE and 95% CI, within each subgroup. The significance level of the treatment group-by-subgroup factor interaction term will be also provided for each factor for descriptive purpose. Forest plots will be provided.

Subgroups of interest are (providing sufficient number of patients per subgroups):

- Baseline normalized TAV(<Median,  $\geq$  Median) for this specific subgroup factor, the ANCOVA model will include this categorical baseline instead of continuous baseline;
- BMI (<25,  $\geq$  25 kg/m^2);
- Weight (<Median,  $\geq$ Median kg) ;
- Gender;
- Age (<65,  $\geq$ 65 years);
- Randomization strata as per registration center (With/Without statin at ACS onset);
- Diabetic status at baseline (Yes, No);
- Diabetic status at baseline relevant to insulin use (No diabetes, diabetes without insulin, diabetes with insulin);
- Diabetic status at baseline relevant to time from diagnosis of diabetes (No diabetes, diabetes for <Median years, diabetes for  $\geq$  Median years);
- Index ACS event (STEMI, NSTEMI, UA);
- Prior ischemic stroke(Yes, No);
- eGFR (<60,  $\geq$ 60 mL/min/1.73m^2) ;
- eGFR (<30,  $\geq$ 30 to <60,  $\geq$ 60 mL/min/1.73m^2); if sufficient number of patients in category  $\geq$  30 to <60, then combine category  $\geq$  30 to <60 and  $\geq$ 60; i.e. eGFR(<30,  $\geq$ 30);
- Baseline calculated LDL-C (<80,  $\geq$ 80 to <100,  $\geq$ 100 to <130,  $\geq$ 130 to <160,  $\geq$ 160 mg/dL) (ie, <2.07,  $\geq$ 2.07 to <2.59,  $\geq$ 2.59 to <3.37,  $\geq$ 3.37 to <4.14,  $\geq$ 4.14 mmol/L);
- Baseline calculated LDL-C (<100,  $\geq$ 100 to <130,  $\geq$ 130 to <160,  $\geq$ 160 mg/dL) (ie, <2.59,  $\geq$ 2.59 to <3.37,  $\geq$ 3.37 to <4.14,  $\geq$ 4.14 mmol/L);
- Baseline HDL-C (<40,  $\geq$ 40 mg/dL) (ie, <1.04,  $\geq$ 1.04 mmol/L);
- Baseline fasting TGs (<150,  $\geq$ 150 mg/dL) (ie, <1.7,  $\geq$ 1.7 mmol/L [mixed dyslipidemia]);
- Baseline Lp(a) (<30,  $\geq$ 30 to <50,  $\geq$ 50 mg/dL) (ie, <0.3,  $\geq$ 0.3 to <0.5,  $\geq$ 0.5 g/L);
- Baseline Lp(a) (<50,  $\geq$ 50 mg/dL) (ie, <0.5,  $\geq$ 0.5 g/L);

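### Culprit versus non-culprit imaging is left open at entry and has no adjusted or subgroup analysis; it enters the efficacy analysis only through a per-protocol criterion that contradicts inclusion criterion I 03

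*Protocol*

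**What the plan says.** In the design rationale (protocol section 4), the sponsor notes that Japanese IVUS studies were shorter than those of a US group yet still showed benefit, and comments: "This may be because differences in target population (ACS vs. non-ACS) and target vessel (culprit vessel vs. non-culprit vessel". The same paragraph mentions diabetes as another setting in which intensive LDL-C lowering may do more.

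I 03 (synopsis and protocol 7.1) leaves the choice of imaged segment to the physician: "regardless of culprit vessels or not culprit vessels) other than the culprit lesions". The follow-up scan is done in the same vessel (protocol section 10).

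Randomization is stratified only by statin use at ACS onset (protocol 8.4). The primary analysis is an ANCOVA "model with treatment arm and randomization strata as fixed effects, and the baseline normalized TAV as covariate"; protocol 11.4.2.1 and SAP 2.4.4.1 agree. Neither the multiple-imputation model nor the subgroup list, introduced by "Subgroups of interest are (providing sufficient number of patients per subgroups", contains a vessel factor. The list does contain diabetes, in three forms, and type of index ACS event.

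Culprit vessels and IVUS locations are collected at Visit 1 (protocol 10.1.1.1). SAP 2.1.1 lists both as baseline disease characteristics, including "Location of analyzed IVUS imaging vessels (RCA, LAD, LCX, Other", and SAP 2.4.1 gives descriptive between-arm p-values for such characteristics.

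SAP 2.3.1.2 removes from the per-protocol population patients who fail certain inclusion criteria. Its version of the imaging criterion says IVUS should be done in the culprit vessels. The primary endpoint and the secondary IVUS endpoints are analyzed on that population as support (SAP 2.4.4.1 and 2.4.4.2).

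**The concern.** Of the factors that this paragraph of the rationale raises, diabetes and ACS both have a counterpart in the subgroup list. Vessel type does not, and no reason is given. It is fixed before randomization and can be derived from collected data.

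Three things are at stake:

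- If vessel type predicts plaque change, a chance imbalance between arms moves the estimate, and no planned model adjusts for it.
- If it modifies the treatment effect, the primary result is an average over whatever mix the sites produced, and no planned analysis shows the effect by vessel type.
- The one efficacy analysis that does depend on vessel type uses a criterion at odds with I 03. A patient correctly enrolled with a non-culprit vessel could be dropped as a major deviator, so the size and meaning of the per-protocol set depend on which text the programmer follows.

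**Working it through.** **Inputs from protocol 11.1.** "it is assumed that difference in percent change in normalized TAV from baseline between alirocumab arm and SoC arm is 8" percentage points; "the common standard deviation of percent change in normalized TAV is 15" points; 75 evaluable patients per arm and 90% power "to detect the treatment difference with two-sided significance level of 5" percent; 25% non-evaluable.

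**Inputs not in the documents (assumed).** The non-culprit share p, the difference d in mean percent change between vessel types, and any difference in treatment effect between them. Ranges are shown.

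**1. The plan's own figure.** SE = 15 × √(2/75) = 2.45. The noncentral t-test with difference 8 and 75 per arm gives power 0.9006. Enrolment is 150 / (1 − 0.25) = 200. Both stated figures reproduce, and neither depends on vessel type.

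**2. Precision from adjusting.** Explained variance R² = d² × p(1 − p) / 15². Residual SD = 15 × √(1 − R²). With p = 0.5:

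| d (points) | R² | Residual SD | Cut in SE | Power at 75 per arm |
|---|---|---|---|---|
| 3 | 9 × 0.25 / 225 = 1.0% | 14.92 | 0.5% | 90.3% |
| 5 | 25 × 0.25 / 225 = 2.8% | 14.79 | 1.4% | 90.8% |
| 8 | 64 × 0.25 / 225 = 7.1% | 14.46 | 3.6% | 92.0% |
| 10 | 100 × 0.25 / 225 = 11.1% | 14.14 | 5.7% | 93.1% |

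The gain is about 2 points of power at d = 8 and 3 at d = 10.

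**3. Chance imbalance.** SD of the between-arm difference in vessel mix = √(p(1 − p) × 2/75) = √(0.25 × 2/75) = 0.082. An imbalance of one SD shifts the unadjusted difference by 0.082 × d: 0.2 points at d = 3 and 0.8 at d = 10, against the SE of 2.45.

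**4. Conditional effect on the average.** Suppose, without support in the documents, that the 8 points applied to culprit vessels only and the non-culprit effect were 4. The average would be 8(1 − p) + 4p. At p = 0.25 that is 7 points (power 81%); at p = 0.5 it is 6 points (power 68%).

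**5. What an interaction test could show.** With p = 0.5 there are 37.5 patients per arm and vessel type, so SE = 15 × √(2/37.5 + 2/37.5) = 4.90. By normal approximation, power is about 13% for a 4-point difference in effect and 37% for an 8-point difference.

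**6. The two criteria side by side.** I 03 accepts any imageable vessel, culprit or not, outside the culprit lesion. SAP 2.3.1.2 calls for the culprit vessel. A patient imaged in a non-culprit vessel meets the first and fails the second. Applied as written and ignoring other exclusions, the SAP text leaves 75 × 0.75 ≈ 56 per arm at p = 0.25 (power about 80% for 8 points), or 75 × 0.5 ≈ 37 per arm at p = 0.5 (about 62%).

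**The case against.** The best defence has four parts.

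- **The rationale is hedged.** It says "may be", names two factors, and compares trial programmes rather than patients within this trial. The 36-week duration rests on earlier Japanese study durations, routine angiographic follow-up and expected drop-out. The choice of Japanese effect sizes rests on differences in IVUS methods. This stands. A reader might infer that the protocol identifies the culprit vessel as a driver of the result, but the text does not go that far.
- **Vessel type is not ignored.** Both locations are summarized and compared at baseline, and on its wording the per-protocol analysis is confined to culprit vessels. The first half stands. The second does not fill the gap. That population also excludes for adherence, scan timing, vessel length and other criteria, and is analyzed by treatment received, so a difference from the mITT result could not be attributed to vessel type.
- **Nothing is biased and the gain is small.** This stands. The arms are randomized 1:1, the same vessel is scanned twice, and treatment, stratification factor and baseline value make a standard ANCOVA. Ordinary imbalance is already covered by the confidence interval.
- **A new term would not rescue a diluted effect.** Also correct. A main-effect covariate does not restore a smaller average, and the interaction test is weak. But the SAP already reports subgroup interactions descriptively for many factors under the same limitation.

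**Conclusion.** The point holds as a gap in pre-specification together with a contradiction between documents. Vessel type is raised in the rationale, left open at entry and recorded, yet has no adjusted or subgroup analysis. Its one role in the efficacy analysis rests on a criterion that conflicts with I 03.

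The statistical size is modest: at most about 2 to 3 points of power, and that requires vessel types to differ by 8 to 10 points at an even mix, which is as large as the whole assumed treatment effect or larger. The stated sample size and power stand.

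A reader might infer that the trial is underpowered, with power near 68%, because non-culprit imaging dilutes the planned effect. The documents do not support that. They do not give the vessel mix in the two studies behind the 8 points, so that figure may already be a mixed average, and they give no expected mix for this trial. Nor do they support a claim of bias in the primary comparison.

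**What to change.** Before database lock:

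1. Derive a baseline indicator for whether the imaged vessel is the culprit vessel (Yes/No) from the two recorded locations. Include a rule for multiple or undetermined culprits and for the category Other.
2. Add it to the subgroup list in SAP 2.4.4.1 as a descriptive factor, and state that the interaction test has low power.
3. Pre-specify a supportive ANCOVA adding this factor for percent change in normalized TAV and absolute change in PAV. Leave the primary model unchanged.
4. Reconcile the imaging criterion in SAP 2.3.1.2 with I 03, so that it is clear whether a patient validly enrolled with a non-culprit vessel belongs in the per-protocol population.

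The cost is SAP wording, one derived variable with its rules, and one extra degree of freedom in a supportive model. No new data are needed, and the sample size and type I error control are untouched.
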